MetricWire, developed and owned by MetricWire Inc., has previously been utilized in clinical and academic research and is HIPPA compliant. Subjects will initially complete a training session which will last up to an hour and 30-minutes, where we will assist in installing the MetricWire app on their smartphone device. They will use the app to report their daily experiences throughout the study. They will be given instructions on how to operate the smartphone app and a guide that they may take home with them that will outline the information covered in the training session. They will also be given contact information should they have any problems or questions with the smartphone app over the course of the study. It will be explained

that all data on the app is encrypted and that the data is sent to a secure server where data is identified by subject id only. Subjects will also be informed that we will be monitoring the upload of data from the smartphone app to the secure server in order to verify that everything is working correctly. Subjects will be asked to use this app to report their mood, stress and alcohol use, once daily in the evening, for the course of the study. It will take approximately 10-15 minutes to complete these assessments each day.

Subjects will receive contingency management for each visit and 1 counseling session per week. As part of this process, participants will provide urine screens and breathalyzer samples twice per week. Blood draws of 15mL of whole blood each will also be done at weeks 2 or 5 and 7 of the study to measure pregnenolone levels. Subjects will also have the option to visit a Quest Diagnostics location to provide blood and urine specimens. These levels will allow staff to ensure subjects are taking medication as prescribed.

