Medication compliance will also be monitored through the use of riboflavin as a marker. Riboflavin produces a bright yellow discoloration of the urine when the medication is taken 2 to 8 hours prior. During the study, staff will easily be able to visually inspect the subject's urine to determine whether the morning dose has been taken. 25mg of riboflavin will be added to all doses of pregnenolone and placebo by the pharmacist when capsules are made. Medication compliance will also be implemented through video Directly Observed Therapy (DOT) using the smartphone application eMocha. Subjects will use the eMocha app to video record themselves taking their medication. Research staff will log into a secure site to view the recorded videos to assess medication dose adherence.

Individual Counseling:

Subjects will participate in once weekly standard individual drug counseling as outlined in the Individual Drug Counseling Manual (IDC, Mercer & Woody, 1994) during the treatment phase in order to support treatment. Each subject will be seen by a Yale Stress Center staff counselor with expertise in IDC who will see the patient for the clinical component of the treatment research phase. The general purpose of the counseling sessions as described in the manual are to: (1) acquire information about important concepts and aspects of recovery from addiction; (2) increase self-awareness of specific problems and issues in relation to addiction and recovery, and (3) learn new coping skills to deal with problems contributing to or resulting from the addiction and to improve functioning. The focus of this psycho-educational approach is on providing patients with frequent supportive contact, introduce them to key concepts about the recovery approach, and develop a sense of personal responsibility for recovery.

**Participants will provide urines 2x/week to assess drug use, and they will receive contingency management for showing up on each of the twice/weekly appointments. Primary outcomes measures will be alcohol use, mood, stress and craving as assessed by MetricWire and urines.

After completion of the study, subjects will be referred to aftercare at the Substance Abuse Treatment Unit (SATU).

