During each laboratory session, about 120mL of whole blood will be drawn to measure stress hormone levels that may change during the session, totaling 360 mL for all three laboratory sessions. The amount of blood drawn over three laboratory sessions is equal to a little over onehalf the blood obtained during a regular blood donation. In addition, 32 mL of whole blood will be drawn on the first day of laboratory session to look at genetic markers, and 10mL of whole blood will be drawn during the physical exam/admission procedure to assess eligibility and look at molecular adaptations during the study. Lastly, 15 mL of whole blood will also be drawn each at weeks 2, 5 and 7 to measure pregnenolone levels. These levels will allow staff to ensure subjects are taking medication as prescribed. Thus, a total amount of 432 mL of whole blood will be drawn throughout the entire study. People who are in good health are not usually affected by this kind of blood loss. However, to be safe, subjects will be warned against donating blood for at least eight weeks after completing this study and 5 weeks beforehand.

III) Laboratory Sessions:

(1). Intravenous (IV) Catheter: When an IV is started, there is some risk that subjects may develop a bruise or bleeding where the vein is punctured. If this occurs, appropriate treatment will be instituted immediately. On extremely rare occasions, fainting, blood clot or infection may occur.

(2). The Imagery Procedures: The imagery method involves reliving a personal stressful event and can be somewhat anxiety provoking at the time of the task. Our previous experience has shown that once the task is over, there is very little anxiety that carries over, thus posing minimal risk. The alcohol cue imagery involves reliving a personal experience involving alcohol-related stimuli associated with alcohol use. While subjects may feel aroused by the alcohol cue imagery, relaxation procedures have been shown to be successful in reducing the physiological arousal associated with cue exposure and stressful imagery. It is likely that moderate craving for alcohol may occur due to subjects' imagining and reliving stressful events and drug cue related events. It is also possible that craving for alcohol may linger even after the task. In order to ensure that subjects are not put at increased risk for alcohol consumption after the laboratory sessions, the following safeguards will be taken:

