Medication compliance will be monitored by blood draws done at weeks 2, 5, and 7, to measure PREG levels, and through the monitoring of riboflavin as a urine marker. Riboflavin produces a bright yellow discoloration of the urine when the medication is taken 2 to 8 hours prior. Subjects will be taking morning and bedtimes doses of the medication. After this time, staff will easily be able to visually inspect the subject's urine to determine whether the morning dose has been taken. 25mg of riboflavin will be added to all doses of PREG and PLA by the pharmacist when capsules are made.

Subjects will self-administer study medication, and will be reminded via daily smartphone platform monitoring. Daily smartphone monitoring will be used to prompt patients to take study medication, and also to assess alcohol use, craving, craving resistance and mood states. Concordance between daily smartphone reports and alcohol positive urines will be evaluated for daily versus retrospective reporting.

Medication compliance will also be implemented through video Directly Observed Therapy (DOT) using the smartphone application eMocha. Subjects will use the eMocha app to video record themselves taking their medication. Research staff will log into a secure site to view the recorded videos to assess medication dose adherence.

All participants and study staff will remain blind to medication condition.

b) Is the drug provided free of charge to subjects? Yes No If yes, by whom?

4. Storage, Preparation and Use: Describe the method of storage, preparation, stability information, and for parenteral products, method of sterilization and method of testing sterility and pyrogenicity.

Commercially available pregnenolone and matching placebo will be obtained, formulated and packaged by Yale IDS Pharmacy in weekly bubble packs for self administration by subjects. Medication and placebo be stored at the Yale Stress Center in our designated medication room in a locked cabinet. Access will be provided to the research nurse, [name], the study physician, [name], and study PI and Co-I, [name] and [name]. Self-administration and dispensing will be conducted by the research nurse or coordinator.

Check applicable Investigational Drug Service	utilized:
 YNHH IDS	 Yale Cancer Center
 CMHC Pharmacy	 West Haven VA
 PET Center	
 Other:	
	None

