All de-identified data will be available to the research investigator PI, Co-Investigator, statistician, DSM, research staff responsible for entering data, NIH/NIAAA, Yale HRRP, and Yale's HIC. Protected Health Information will be available to the research physician, and research staff only when deemed necessary.

g. If appropriate, has a [Certificate of Confidentiality](#) been obtained?

A Certificate of Confidentiality has been obtained from the National Institutes of Health.

h. Are any of the study procedures likely to yield information subject to mandatory reporting requirements? (e.g. HIV testing – reporting of communicable diseases; parent interview -incidents of child abuse, elderly abuse, etc.). Please verify to whom such instances will need to be reported.

Mandatory reporting of incidents of abuse or neglect of a child or elderly person as required by Connecticut State law will be complied with. Additionally, certain reportable infectious diseases such as HIV and Hepatitis B and C will be reported to the appropriate state agency, although these will not be tested by the study. We may also need to intervene and report information regarding threat of injury to self or others to the proper authorities. All of these requirements will be complied with.

SECTION IX: POTENTIAL BENEFITS

Potential Benefits: Identify any benefits that may be reasonably expected to result from the research, either to the subject(s) or to society at large. (Payment of subjects is not considered a benefit in this context of the risk benefit assessment.)

The proposed study has the potential to reveal novel mechanisms that may play a role in alcohol addiction. A better understanding of alcohol use disorder is of utmost importance in order to develop improved treatments for alcohol use disorders. Understanding the potential role of neuroactive steroids in alcohol addiction could also aid in our knowledge of the role of sex hormones and their precursors and derivatives in this disorder, and thereby allow us to potentially address gender differences that exist in the development, progression and relapse of alcohol use disorder.

SECTION X: RESEARCH ALTERNATIVES AND ECONOMIC CONSIDERATIONS**1. Alternatives:** What other alternatives are available to the study subjects outside of the research?

Subjects need not participate in this study to receive treatment for alcohol use disorder, such as approved pharmacotherapies and counseling, group therapy, and psychotherapy.

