2. Payments for Participation (Economic Considerations): Describe any payments that will be made to subjects, the amount and schedule of payments, and the conditions for receiving this compensation.

Subjects completing the Study will receive \$20 for a remote intake interview session or \$25 for an in-person intake interview session, \$25 for the imagery and relaxation training session, and \$100 for each of the 3 laboratory sessions. Subjects will also be paid a \$50 bonus for completing the laboratory sessions. Therefore, for the completion of all procedures leading up to and including the laboratory sessions, subjects will receive up to a total of \$400.

If subjects continue on to complete the treatment phase, they will earn chances to win dollar prizes for kept appointments to encourage appointment attendance. For every twice/weekly appointments they attend, the chance to draw a prize from the fishbowl will increase by one. The fishbowl prizes are in increments of \$1, \$5, \$20, and \$100. Subjects will participate in this at every twice/weekly appointment they attend. If they miss any appointment, or fail to take study medication, the chances will be reset back to one. For example, if no appointments are missed the subject will have a total of 8 chances at the last appointment. Each prize increment that is won from the 8 attempts is then added together into a lump sum. There is no limit on the amounts that can be won. A standard payment rate of \$20 per week can be used in lieu of drawing from the fish bowl in order to encourage completion of appointments.

Subjects participating in smartphone monitoring will be compensated for their participation at \$2 a day, with a \$6 bonus for completing all 7 days, hence a possible total of \$20 a week, or \$160 for all 8 weeks of the study. Subjects will receive \$25 per week for taking study medication using eMocha for a total of \$200 for completing all 8 weeks. In addition, subjects will receive \$25 for week 3, \$25 for week 5, \$25 for week 7, and a \$25 bonus for completing the treatment phase. The total that subjects may be reimbursed if they complete all aspects of the study will be \$860 plus the various amounts won for keeping appointments during the treatment phase.

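### Staff are to check adherence with blood levels of the study drug while remaining blind, and nothing in the plan masks or holds the results: an unblinding risk of unknown size

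*Combined protocol and SAP*

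**What the plan says.** Three places in the combined protocol and SAP give the treatment-phase pregnenolone level the same job.

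- Section V.3 (General Procedures, treatment visits) says 15 mL draws "will also be done at weeks 2 or 5 and 7 of the study to measure pregnenolone levels", and adds "These levels will allow staff to ensure subjects are taking medication as prescribed".
- Section V.9 (II, Drawing of Blood) lists draws at weeks 2, 5 and 7 and repeats that sentence.
- Section VI.A.3 (Source) says "Medication compliance will be monitored by blood draws done at weeks 2, 5, and 7, to measure PREG levels".

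Section VI.A.3 also carries the blinding rule: "All participants and study staff will remain blind to medication condition". It names no exception.

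The plan has two further adherence checks, and both work in every arm. Riboflavin (25 mg) goes into all active and placebo capsules, and participants record themselves on video taking each dose (Sections V.3 and VI.A.3).

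On sample handling, Section V.3 (HPA and Catecholamine Measures) keeps laboratory-session tubes at -70C before transport. The Neuroactive Steroid Measures paragraph sends pregnenolone, allopregnanolone and androstanediol to a separate Yale facility. For treatment visits, Section V.3 adds "Subjects will also have the option to visit a Quest Diagnostics location to provide blood and urine specimens". How the treatment-phase steroid results are reported, to whom and when is not described.

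**The concern.** A drug level is a good adherence check for someone who knows the allocation. For someone who does not, it is a clue to the allocation. Staff who follow the plan as written would be reading a marker that differs by design between active drug and placebo, while being told to stay blind.

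The outcomes at stake are those that depend on staff judgement or on contact between staff and participant. Section V.12 names the Substance Use Calendar and SAFTEE adverse events among the primary measures. A research assistant assesses substance use by structured interview and self-report (Section V.3, Assessments). Study staff and investigators evaluate adverse events (Section V.3, Safety and Side Effects Measures). The investigator classifies seriousness, and relatedness to the agent is a graded judgement (Section V.11). Section V.12 intends the results to supply effect sizes for a larger trial, so any bias would be carried forward.

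**Working it through.** The plan gives no figure for this risk, so there is none to reproduce. The check is a comparison of the text plus some counts.

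**1. Can the adherence rule and the blinding rule both be followed?** To use a level, staff must see the value or a report derived from it. The plan names no unblinded reader, no adherent/non-adherent report and no hold on results. If results were held, the sentence in Sections V.3 and V.9 could not be carried out as written. The two rules need a bridging rule, and none is given.

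**2. What would a level reveal?**
- A raised level points to active drug.
- A low level alone is ambiguous. Pregnenolone occurs naturally (Section VI.A.1), and an active participant may have missed doses.
- A low level with positive riboflavin and observed dosing points to placebo. The two other checks remove the ambiguity.

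**3. How many results are involved?** Allocation is 30 per arm, 90 in total (Section V.3, Study Design and Overview).
- Two draws each, one reading of Section V.3: 90 × 2 = 180 results, of which 30 × 2 = 60 are from placebo.
- Three draws each (Sections V.9 and VI.A.3): 90 × 3 = 270 results, of which 30 × 3 = 90 are from placebo.
- Either way one third cannot show adherence, because there is no study drug to detect.
- The laboratory sessions add 360 mL / 15 mL = 24 samples per participant (Table 1 note), and pregnenolone and allopregnanolone are measured at each time point. Section V.2 reports that allopregnanolone rose markedly on the drug in earlier studies, so those results could also reveal the arm.

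**4. Can the risk be sized?** No. The documents give no pregnenolone concentration, SD or assay precision by arm. To show how far the answer depends on that, assume unit-SD normal levels, an active-placebo shift of d SD, one result and every dose taken. With two thirds on active drug, the best cut-off is t = d/2 − ln(2)/d, and the share of arms guessed correctly is (2/3)Φ(d − t) + (1/3)Φ(t).
- d = 0.5: 67.5%
- d = 1: 73.0%
- d = 3: 93.8%
- Always guessing active: 60/90 = 66.7%

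The result runs from almost no gain to near-complete unblinding on an assumed input. It shows only that the size is unknown, and it is not used to grade the point.

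**The case against.** The strongest reply is that nothing shows a numeric level reaching an outcome assessor during treatment. The blinding rule is explicit, the steroid assay is done at a separate facility, and frozen storage fits batched assay after the trial. The mechanism could be left to operating procedures. This stands as far as it goes: the point is a risk, not an event. It does not answer the sentence that assigns the levels to staff as an adherence check. The storage text concerns laboratory-session tubes, and handling of the treatment-phase draws is not described.

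It is also fair to say that the consequence is limited. This is a pilot with mostly descriptive analysis, and Section V.3 says "Primary outcomes measures will be alcohol use, mood, stress and craving as assessed by MetricWire and urines", which are less exposed. Participants are blind when they report drinking, and the unaffiliated monitoring board reviews adverse events. That board does not mask the person who takes the interview.

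Two stronger readings are tempting and are not supported.

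- **Release of values during the trial.** Section VIII says "All de-identified data will be available to the research investigator PI, Co-Investigator, statistician, DSM, research staff responsible for entering data", and a reader might infer that levels are released to the investigators while the trial runs. That sentence answers a privacy question about who may hold identifiable and de-identified data, and it gives no timing. It neither releases nor withholds assay values.
- **Lost prize chances.** Section X.2 says "If they miss any appointment, or fail to take study medication, the chances will be reset back to one", and a reader might infer that a placebo participant who took every dose could lose chances because of a low level. The section names no signal. Prizes are drawn at twice-weekly visits (2 × 8 = 16 over 8 weeks), against two or three blood draws, so the level could hardly be the routine trigger.

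**Conclusion.** The point holds as an unblinding risk of unknown size that should be fixed. Staff are told to use levels of the study drug while remaining blind, and the published text contains no mask, restriction or hold. In 30 of 90 participants the level cannot do the job given to it.

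A reader might go further and conclude that the trial is unblinded. The documents do not support that. They do not say when results return or which staff see them, and they give no levels by arm.

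The conclusion rests on two assumptions: that the adherence sentence means what it says, and that no restriction exists in a document outside the published text. The exposure is greatest for the Substance Use Calendar, where it is taken by interview, and for the SAFTEE and adverse-event judgements.

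**What to change.** Replace the adherence sentence in Sections V.3 and V.9, and amend Section VI.A.3, along these lines:

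> Pregnenolone and neuroactive-steroid results from all post-randomisation draws, including any taken at an outside laboratory, are withheld from site staff and investigators until database lock. Adherence during the trial is checked with the riboflavin marker and video-observed dosing.

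The hold covers the steroid assays only. The safety chemistry at weeks 2, 5 and 7 (Section V.3, Safety and Side Effects Measures) is not affected.

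State also how the levels are used after unblinding. As an adherence measure they apply to the two active arms only. The planned allopregnanolone comparisons and mediation analyses against placebo (Aims 2a, 2b and 3b) keep all three arms.

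The number of draws should be reconciled at the same time. The stated blood total of 432 mL equals 360 + 32 + 10 + 2 × 15, whereas the three draws listed in Section V.9 give 360 + 32 + 10 + 3 × 15 = 447 mL.

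The cost is a few sentences and an instruction to each laboratory that assays or reports these samples. The downside is the loss of one in-trial adherence signal. Riboflavin as described shows only the morning dose, so video must cover the bedtime dose.

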Once a subject is deemed eligible, signs consent and completes all intake assessments, s/he will be randomized to 300mg PREG, 500mg PREG, or PLA and exposed to three laboratory sessions as close together as possible of guided imagery of stress, drug cues and neutral-relaxing cues in week 2 (identified as lab DAY 1, DAY 2, and DAY 3). In a session prior to laboratory sessions, subjects will participate in an imagery script development to provide descriptions of recent stressful, drug cue related and neutral relaxing situations to the research assistant. On the day before laboratory session 1 , subjects will participate in a relaxation and imagery training and IV habituation session, followed by three laboratory sessions that include IV blood drawing.

Daily surveys using a Smartphone platform (MetricWire) monitoring will prompt subjects to take study medication, and provide responses on their alcohol use, craving, stress and mood states for the day (see below for detailed description).

Genetic studies:

Ten mL of whole blood will be collected during physical examination to assess eligibility, and thirty-two mL of whole blood will be also collected from patients on the day of the first laboratory session (LAB DAY 1) for the purposes of understanding genetic factors that may affect craving.

Throughout the 8 week study, subjects will self-administer 300mg/day, 500mg/day or PLA/day and study staff will provide weekly medication packs to subjects.

Participants will be seen twice per week at the Yale Stress Center at [name] to receive once/week counseling, provide urine and receive contingency management for treatment attendance. Daily surveys using the smartphone platform (MetricWire) monitoring will prompt subjects to take study medication, and provide responses on their alcohol use, craving, stress and mood states for the day. Smartphone data will be collected daily. Subjects will be prompted at two random times in the morning and afternoon to complete a brief 1-minute survey of questions and a third 5-10 minute survey to be completed at night before bedtime. The surveys are set up with standard automated questions and prompts and subjects will use the smartphone key pad to answer the prompts (via MetricWire).

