Laboratory Sessions. In week 2 of the study PREG/PLA administration and hence DAY 1, 2 and 3 of the laboratory portion of the study, subjects will be brought into the research testing rooms of the Yale Stress Center (YSC) at 2:00 PM. The laboratory sessions will only be conducted if the subject has a breath alcohol level of 0, otherwise the session will be rescheduled. The subject will then be prepared for physiological assessments. An indwelling intravenous (IV) catheter will be inserted by the research nurse specialist in the antecubital region of the subject's non-preferred arm for blood sampling. Blood samples will be obtained periodically for assessment of neuroactive steroids, ACTH, cortisol, prolactin, NE and EPI levels. A blood pressure cuff will be placed on the subject's preferred arm to monitor blood pressure (BP) periodically. On-line assessment of physiological measures will be obtained at specified time periods during the laboratory sessions. Self-reports of emotional state, anxiety and alcohol craving will also be assessed periodically.

After preparation of assessments and a 40 minute adaptation period, two blood draws before imagery will be conducted (BASELINE). After the second blood draw, a 5-minute baseline period will follow to assess continuous pulse rate and BP assessments. Following the baseline period, instructions for conducting imagery will be provided. The order and content of the imagery condition will not be revealed to the subject or to the research staff conducting the

sessions. In the imagery task the subjects will be asked to imagine the situation being described vividly, 'as if it were happening right now", until asked to stop. The imagery script will be played to the subject over headphones and the subject will be required to imagine the situation for 5 minutes. A tape recording for each subject's script will be developed prior to the testing situation and recorded by the same person for each subject. Immediately following imagery, a blood draw will be conducted (IMAGERY). Thereafter, four recovery blood draws will be conducted at 15 minute intervals (RECOVERY). Timeline for assessments is detailed in Table 1.

TABLE 1: Schedule for Laboratory Sessions

LAB DAY 1 11AM: Imagery and Relaxation Training and IV Habituation session (1 hour)

LAB DAY 1, 2 and 3: LABORATORY (IMAGERY) TESTING SESSIONS

2:00 PM	Set-up for plasma (IV insert) measures; physiological Setup - HR, BP, Finger Temp, SCL.

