For both HPA and catecholamine assays, data will be analyzed for the time-points outlined in Table 1. In addition, as each measure may show different response profiles over time, we will also assess maximal or peak response and area under the curve (AUC) for each measure. Peak and AUC assessments of these measures are commonly used methods to reduce variability in responses and have been used in several studies (Kirschbaum, Wust, Faig, & Hellhammer, 1992; O'Malley, Krishnan-Sarin et al. 2002).

d. Neuroactive Steroid Measures. To assess plasma levels of pregnenolone, allopregnanolone and androstanediol, a 1mL of plasma will be collected at each timepoint, and processed as per above. Analysis of these neuroactive steroids will be conducted at The Chemical Instrumentation Center at Yale, which has a state of the art gas chromatography/ mass spectrometry (GC/MS) instrumentation (Agilent 5973 GC-MS w/autosampler, HP 5971A GC-MS) following procedures outlined in Milivojevic et al., 2016).

Assessments: A trained research assistant will meet with the client at various time-points to assess the client on selected substance use and psychological functioning measures using structured interviews, self-report assessments and to obtain urine samples (at the Yale Stress Center) for toxicology screens. A description of the assessment battery follows.

Screening Assessments:

Assessment of IQ and Executive Functioning. *The Shipley Institute of Living Scale (Shipley 1940)* is a paper and pencil test taking about 15-20 minutes to complete. It consists of two parts (vocabulary and abstraction) which when combined provides a global measure of cognitive functioning and IQ. The Shipley will be administered to ensure that subjects will be able to successfully participate in the self-report components and comprehend all aspects of the protocol.

Sociodemographic/general patient information. Demographic data, medical history, and family psychiatric history will be assessed with interviews and self-report forms that provide data on age, race, socioeconomic status, marital status, psychiatric family history, educational and occupational levels, and significant medical history.

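### The stated blood total of 432 mL does not follow from its own items (447 mL), and counting Table 1's 25 cc draws gives 462 to 537 mL

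*Combined protocol and SAP*

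**What the plan says.** Section V, item 9 (Risks, Drawing of Blood) builds up the total. For each session, "about 120mL of whole blood will be drawn to measure stress hormone levels", which it puts at 360 mL over three sessions. It adds 32 mL on the first laboratory day for genetic markers and 10 mL at the physical. Then: "Lastly, 15 mL of whole blood will also be drawn each at weeks 2, 5 and 7 to measure pregnenolone levels". It concludes: "Thus, a total amount of 432 mL of whole blood will be drawn throughout the entire study".

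Other sections bear on the same items:

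- **Level draws.** Section VI.A.3 agrees on three: "Medication compliance will be monitored by blood draws done at weeks 2, 5, and 7, to measure PREG levels". Section V, item 3 (General Procedures) is ambiguous: "Blood draws of 15mL of whole blood each will also be done at weeks 2 or 5 and 7".
- **Session draws.** Table 1 lists eight per session: initial, baseline, post-image and Recovery 1 to 5. It marks the initial, post-image and Recovery 3 draws as 25 cc, of which 10 cc is for RNA. Its heading covers laboratory days 1, 2 and 3. The note below the table and the HPA and Catecholamine Measures paragraph both give 15 mL per time point and 360 mL over three days.
- **Recovery draws.** The Laboratory Sessions text says "Thereafter, four recovery blood draws will be conducted at 15 minute intervals (RECOVERY", one fewer than Table 1 and than the time factor in Section V, item 12. That text refers the reader to Table 1 for the timeline.
- **Genetic sample.** Section V, item 4 says the 32 mL is taken apart from the session draws.
- **Limit.** The HPA and Catecholamine Measures paragraph says the blood drawn is within a guideline of 450 mL in 8 research weeks. The sentence comes straight after the 360 mL session figure.

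**The concern.** The total is presented as the sum of the items before it, and it is not that sum. It is also the blood-loss figure on which the risk section relies when it reassures the reader about people in good health.

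There are two separate faults. One is an addition that does not close. The other is an input, the 360 mL, that does not match the sampling schedule it is meant to summarise. The first fault alone keeps the total under 450 mL. The second matters more, because on some readings the scheduled volume passes the limit that the protocol says it respects.

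**Working it through.** **1. The plan's own figure.** Inputs from Section V, item 9: sessions 360, genetics 32, physical 10, level draws 15 each.

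- Three level draws, as listed: 360 + 32 + 10 + 3 × 15 = 447 mL.
- Two level draws: 360 + 32 + 10 + 2 × 15 = 432 mL.

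The stated total is therefore reproduced exactly with two level draws but not with the three listed. The gap is 447 − 432 = 15 mL, and 15 / 432 = 3.5%.

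There are two ways to arrive at two draws. The General Procedures wording can be read as one draw at week 2 or 5 and one at week 7. Alternatively, the week 2 level could come from session blood: the sessions fall "in week 2 (identified as lab DAY 1, DAY 2, and DAY 3", and pregnenolone is assayed there ("To assess plasma levels of pregnenolone, allopregnanolone and androstanediol, a 1mL of plasma will be collected at each timepoint"). Against both, the risk section describes the level draws as additional and names three weeks, as does Section VI.A.3.

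**2. The 360 mL.** 8 draws × 15 mL = 120 mL per session, and 3 × 120 = 360 mL. This needs every draw to be 15 mL. With Table 1's volumes, five draws at 15 and three at 25 give 5 × 15 + 3 × 25 = 150 mL per session, 30 mL more.

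Whether this applies on every laboratory day is not settled. Table 1's heading covers all three days. Section V, item 4 places the genetic and gene-expression blood at the physical and on laboratory day 1, so day 1 only is a serious reading.

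- Day 1 only: 150 + 120 + 120 = 390 mL of session blood.
- All three days: 3 × 150 = 450 mL of session blood.

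**3. Study totals with the 25 cc entries.** Non-session blood is 32 + 10 + 45 = 87 mL with three level draws, or 32 + 10 + 30 = 72 mL with two.

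| 25 cc entries apply on | Level draws | Total (mL) | Above 432 | Above 450 |
|---|---|---|---|---|
| Day 1 only | 2 | 390 + 72 = 462 | 30 | 12 |
| Day 1 only | 3 | 390 + 87 = 477 | 45 | 27 |
| All three days | 2 | 450 + 72 = 522 | 90 | 72 |
| All three days | 3 | 450 + 87 = 537 | 105 | 87 |

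**4. Sensitivity of the comparison with 450 mL.**

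- If the 10 mL at the physical falls outside the 8 weeks, the four totals become 452, 467, 512 and 527 mL. The first is too close to 450 to call, since the session input is itself approximate.
- If the limit covers session blood only, the comparison is 390 to 450 mL, which does not exceed it.
- The laboratory chemistry at weeks 2, 5 and 7 (Safety and Side Effects Measures) has no stated volume. It is not counted above.

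**The case against.** The strongest reply is that the total may be right and the list wrong. Two level draws give 432 mL exactly, and the General Procedures wording allows two. That is a fair account of where the figure may have come from. It does not remove the fault, because the list in Section V, item 9 and the statement in Section VI.A.3 would then need correcting instead.

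Second, the 25 cc entries may be stray text or may overlap with the 32 mL sample. Table 1's last row continues breath-alcohol checks down to a threshold, although sessions run only at a reading of zero and no drinking is scheduled, so carried-over text is plausible. On day 1 only, the three RNA portions come to 30 cc, close to 32 mL. If they replaced the 32 mL sample, the totals would be 390 + 10 + 30 = 430 or 390 + 10 + 45 = 445 mL, both under 450. However, Section V, item 4 says the 32 mL is drawn separately. On the three-day reading the same substitution still gives 450 + 10 + 30 = 490 or 450 + 10 + 45 = 505 mL. If the entries are stray, no blood is added, but Table 1 still needs correcting.

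Third, the Laboratory Sessions text implies seven draws (2 + 1 + 4). With the 25 cc entries, that count gives 417 to 492 mL, and one combination gives 432. But seven draws at 15 mL give 105 mL per session and 315 mL over three, which contradicts the stated 120 and 360, and the text defers to Table 1.

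Fourth, a breach of the 450 mL limit has not been shown, because its scope is unclear. That stands, and the conclusion is conditional on it.

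**Conclusion.** The concern holds. The risk section's own items sum to 447 mL against a stated 432 mL, and this needs no assumption beyond taking the list as written. The session figure of 360 mL leaves out the extra 10 cc in each of three draws that Table 1 schedules.

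With eight draws per session and the 25 cc entries additional to the 32 mL genetic sample, the study total is 477 or 537 mL with the three level draws listed, and 462 or 522 mL with two. That is 30 to 105 mL above the stated total. If the 450 mL covers the whole study including the physical, these totals exceed it by 12 to 87 mL, and Table 1 does not support the compliance statement. If it covers session blood only, Table 1 at most reaches it.

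This should be fixed because it is a participant-risk figure. Confidence is high in the 447 mL sum and in the conflict between 15 mL and 25 cc. Which total is the true one depends on readings that only the investigators can settle. No outcome analysis is affected.

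**What to change.** Put one list of blood draws in the protocol, with a volume and day for each, and make General Procedures, the Laboratory Sessions text, Table 1 and its note, HPA and Catecholamine Measures, the risk section and Section VI.A.3 agree with it. The list should settle:

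- on which laboratory days the 25 cc entries apply;
- how many level draws there are, and whether the week 2 level uses session blood;
- whether the chemistry at weeks 2, 5 and 7 uses the same samples;
- whether there are four or five recovery draws, so that the Laboratory Sessions text agrees with Table 1 and Section V, item 12.

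Then restate the total from the list and say what the 450 mL covers. If the restated volume is above it on that scope, correct the compliance statement or bring the schedule within it. Which draws and volumes to keep is for the investigators to decide.

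The cost is a text amendment to the protocol, plus the same correction in any other study document that repeats the total. The reconciliation itself requires no change to the design or analysis.
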